20.2. Definitions and Classification

Adverse event definitions are provided in Table 20.2-1. Administrative edits were made on the safety definitions from ISO 14155 and MEDDEV 2.7/3 for clarification purposes.

Table 20.2-1: Safety Definitions

Term	Definition
Adverse Event (AE) Ref: ISO 14155 Ref: MEDDEV 2.7/3	Any untoward medical occurrence, unintended disease or injury, or any untoward clinical signs (including an abnormal laboratory finding) in subjects, users or other persons, whether or not related to the study medical device. NOTE 1: This includes events related to the study medical device or comparator. NOTE 2: This definition includes events related to the procedures involved. NOTE 3: For users or other persons, this definition is restricted to events related to the study medical device.
Adverse Device Effect (ADE) Ref: ISO 14155 Ref: MEDDEV 2.7/3	Adverse event related to the use of the study medical device NOTE 1: This includes any adverse event resulting from insufficiencies or inadequacies in the instructions for use, the deployment, the implantation, the installation, the operation, or any malfunction of the study medical device. NOTE 2: This definition includes any event resulting from use error or intentional abnormal use of the study medical device.
Serious Adverse Event (SAE) Ref: ISO 14155 Ref: MEDDEV 2.7/3	Note: This definition meets the reporting objectives and requirements of ISO 14155 and MEDDEV 2.7/3. Adverse event that: a) Led to death, b) Led to serious deterioration in the health of the subject as defined by either: 1) a life-threatening illness or injury, or 2) a permanent impairment of a body structure or a body function, or 3) in-patient hospitalization or prolongation of existing hospitalization, or 4) medical or surgical intervention to prevent life-threatening illness or injury or permanent impairment to a body structure or a body function c) Led to fetal distress, fetal death, or a congenital abnormality or birth defect.

Table 20.2-1: Safety Definitions

Term	Definition
	NOTE 1: Planned hospitalization for a pre-existing condition, or a procedure required by the clinical investigational plan, without a serious deterioration in health, is not considered a serious adverse event.
Serious Adverse Device Effect (SADE) Ref: ISO 14155 Ref: MEDDEV 2.7/3	Adverse device effect that has resulted in any of the consequences characteristic of a serious adverse event.
Unanticipated Adverse Device Effect (UADE) Ref: 21 CFR Part 812	Any serious adverse effect on health or safety or any life-threatening problem or death caused by, or associated with, a device, if that effect, problem, or death was not previously identified in nature, severity, or degree of incidence in the investigational plan or application (including a supplementary plan or application), or any other unanticipated serious problem associated with a device that relates to the rights, safety, or welfare of subjects.
Unanticipated Serious Adverse Device Effect (USADE) Ref: ISO 14155 Ref: MEDDEV 2.7/3	Serious adverse device effect which by its nature, incidence, severity, or outcome has not been identified in the current version of the risk analysis report. NOTE 1: Anticipated serious adverse device effect (ASADE) is an effect which by its nature, incidence, severity or outcome has been identified in the risk analysis report.
Device Deficiency Ref: ISO 14155 Ref: MEDDEV 2.7/3	An inadequacy of the study medical device related to its identity, quality, durability, reliability, safety or performance. This may include malfunctions, use error, or inadequacy in the information supplied by the manufacturer.

Underlying diseases are not reported as AEs unless there is an increase in severity, location, or frequency, beyond the expected course or progression of the disease, during the investigation. Death should not be recorded as an AE, but should only be reflected as an outcome of a specific SAE.

Hospitalization is defined as any in-patient admission regardless of duration of stay. Emergency room admissions and outpatient visits are not considered hospitalizations.

Any adverse event or complaint occurring in subjects who withdraw participation in the study and opt to remain implanted with the device should be reported to the Complaints Call Center as detailed in the “Directions for Use (DFU)”.

In accordance with FDA regulations 21 CFR 820.3, a complaint is any written, electronic or verbal communication that alleges deficiencies related to the identity, design, quality, durability, reliability, safety, effectiveness or performance of a product after it is released for distribution.

Pregnancy will not be considered an adverse event. If a subject becomes pregnant, she may withdraw from the study or remain in the study at her discretion with concurrence of her physician.

NOTES:

1. For the purposes of this study, hospitalization is defined as any in-patient admission.
2. Hospitalizations occurring for the purpose of performing a planned procedure as per routine care such as implant procedures, or follow-up visits, are not to be reported as a SAE. However, complications or adverse events that occur during the planned procedure should be reported as (S)AEs if they meet the protocol specified definitions.
3. Elective/planned hospitalization(s) need not be reported as an SAE. However, complications or adverse events that occur during an elective/planned hospitalization, should be reported as (S)AEs if they meet the protocol specified definitions.
4. In the event of subject death during the conduct of the study, efforts should be made to perform an autopsy.
5. Sensations or side effects that occur during the programming session should not be reported as AEs. However, sensations or side effects caused by the final programming parameters (including active contact, pulse width, frequency, and amplitude) that persist or occur after the completion of the programming will be reported as AEs.
6. Lack of efficacy/decreased therapeutic response will not be collected as AEs. Also, return of the patient's pain symptoms to their pre-SCS level does not meet the criteria for an AE.
7. Clinically significant worsening of symptoms, beyond the pre-SCS symptoms or the expected course or progression of the disease, should be reported as an AE.
8. Device/lead migration will not be collected as an AE. However, if the device/lead migration precipitated an AE, the AE should be reported in the *Adverse Event* eCRF. Device/lead migration should be documented in the *Device Deficiency* eCRF.
9. Device deficiencies, failures, malfunctions, and product nonconformities should not be reported as adverse events. However, if an adverse event resulted from a device failure or malfunction, that specific event would be recorded on the *Adverse Event* eCRF. Device deficiencies, failures, malfunctions, and product non-conformities should be documented in the *Device Deficiency* eCRF.

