19.4. Possible Interactions with Concomitant Medical Treatments

There are no concomitant medical treatments required outside of standard of care treatment.

19.5. *Risk Minimization Actions*

Additional risks may exist. Risks can be minimized through compliance with this protocol, performing procedures in the appropriate hospital environment, adherence to subject selection criteria, close monitoring of the subject's physiologic status during research procedures and/or follow-ups and by promptly supplying BSC with all pertinent information required by this protocol.

19.6. *Anticipated Benefits*

The reported benefit of SCS is to reduce chronic pain of the trunk and/or limbs. Refer to the Directions for Use for more information. There are no anticipated benefits to the subject for wearing the chest-worn and wrist-worn biosensor and reporting answers to questions on the study-specific smartphone.

19.7. *Risk to Benefit Rationale*

The risk evaluation for BSC neurostimulation systems determined that all hazards attributed to BSC neurostimulation systems and overall remaining residual risks after implementations of the required mitigations have been evaluated. Based on the risk evaluation results, the benefit provided by BSC neurostimulation systems to treat chronic intractable pain of the trunk and limbs outweighs the remaining residual risk. As the overall residual risk meets BSC's criteria, BSC neurostimulation systems are acceptable for use in a clinical setting.

The risk to benefit rationale for study participation is reasonable.

20. Safety Reporting

20.1. *Reportable Events by investigational site to Boston Scientific*

It is the responsibility of the investigator to assess and report to BSC any event which occurs in any of following categories:

- All Serious Adverse Events
- All Device Deficiencies
- Unanticipated Adverse Device Effects
- New findings/updates in relation to already reported events
- All Device Related Adverse Events (Device Hardware and Stimulation Related)
- All Procedure Related Adverse Events

When possible, the medical diagnosis should be reported as the Event Term instead of individual symptoms.

If it is unclear whether an event fits one of the above categories, or if the event cannot be isolated from the device or procedure, it should be submitted as an adverse event and/or device deficiency.

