The investigator must report Device and Procedure Related Adverse Events, Adverse Device Effects, Serious Adverse Events (regardless of relationship to device hardware, stimulation and/or procedure), Unanticipated Adverse Device Effects, and Device Deficiencies for each subject from the time of Information Consent through the end of study participation. AEs and Device Deficiencies may be reported via phone, fax or email if the electronic data capture (EDC) system is unavailable. The paper AE Notification Form or Device Deficiency Notification Form should be used to report AEs and/or device deficiencies during this time.

The Investigator must assess the potential relationship of all adverse events to the study device and/or to study procedures.

- Adverse events must be assessed according to their relationship to one of the following categories:
 - Device Hardware-Related AEs:** AEs that can reasonably (i.e. Unlikely, Possibly, Probably and Causally Related) be attributed to the mere physical presence of the device or to deficiency of the device (i.e., an allergic response to device materials).

- **Stimulation-Related AEs:** AEs that can reasonably (i.e. Unlikely, Possibly, Probably and Causally Related) be attributed to the effects of stimulation. A relationship to stimulation may be determined by demonstrating a predictable response to the alternating between stimulation-on and stimulation-off settings. However, a relationship to stimulation may also be reported without demonstrating a predictable response to the alternating between the stimulation-on and stimulation-off settings if in the opinion of the Investigator the AE is potentially related to stimulation.
- **Procedure Related AEs:** AEs that can reasonably (i.e. Unlikely, Possibly, Probably and Causally Related) be attributed to a study protocol required procedure.

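### Note 5 on programming sessions (NAVITAS 20.2, ENVISION 17.2) contradicts the rules requiring all SAEs and all stimulation-related AEs, so the safety rates may be under-counted and may differ by site

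*Combined protocol and SAP*

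**What the plan says.** Note 5 reads the same in NAVITAS 20.2 and ENVISION 17.2. Its first sentence is an exclusion: "Sensations or side effects that occur during the programming session should not be reported as AEs". Its second sentence restores some reporting, under two conditions. The cause must be the settings left in place ("sensations or side effects caused by the final programming parameters"), and the timing must be after the session ("that persist or occur after the completion of the programming will be reported as AEs"). Seriousness is not mentioned.

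The reporting sections are broader. NAVITAS 20.1 and ENVISION 17.1 list "All Serious Adverse Events" and "All Device Related Adverse Events (Device Hardware and Stimulation Related") as reportable. NAVITAS 20.4 and ENVISION 17.4 add that the duty covers "Serious Adverse Events (regardless of relationship to device hardware, stimulation and/or procedure") and runs from consent to the end of participation.

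The safety parameter in NAVITAS 7.1 and in the ENVISION synopsis is the rate of device- and procedure-related AEs, and of SAEs, from consent to exit.

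**The concern.** Programming tries different contacts, pulse widths, frequencies and amplitudes, and both studies foresee reprogramming visits (NAVITAS 11.22, ENVISION 10.9). It is therefore a recurring setting in which stimulation-related events can arise. Note 5 tells the site not to report what happens there, while the reporting sections tell it to report every SAE and every stimulation-related AE. A coordinator holding both instructions has no rule for choosing between them.

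Neither study has pre-defined endpoints or formal hypotheses, so the AE and SAE rates are the one result each plan commits to in advance. With up to 30 sites in each study, two defensible readings could put the same event in the numerator at one site and leave it out at another.

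**Working it through.** The plan states no figure to reproduce: it gives no expected AE or SAE rate, no number of programming sessions and no safety threshold. The check is to take each type of event through both sets of rules.

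1. **Non-serious, arises and resolves in the session.** Note 5 excludes it. The reportable lists, taken alone, would include it if it is a stimulation-related AE, and NAVITAS 20.3 gives undesired sensations as its example of that category. The exclusion is explicit and looks intended.
2. **Arises in the session and meets an SAE criterion.** Note 5, first sentence: not reported as an AE. NAVITAS 20.1/20.4 and ENVISION 17.1/17.4: reported. The rules conflict.
3. **Arises in the session from a setting that is then dropped, and persists afterwards.** The first sentence of Note 5 excludes it and the second does not bring it back, because the cause is not the final setting. The reportable lists include it if it is stimulation-related, and that category is not limited to final settings (NAVITAS 20.3 and 20.4, ENVISION 17.4). The rules conflict.
4. **Caused by the final setting, and persists or begins after the session.** Reported under both sets of rules.
5. **Caused by a dropped setting, first appears after the session.** The exclusion in Note 5 does not reach it, since it did not occur in the session. The reportable lists apply.

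The conflict is therefore confined to types 2 and 3.

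**Do the neighbouring notes show the gap is deliberate?** They point the other way. Note 2 exempts routine-care hospital stays but adds that "complications or adverse events that occur during the planned procedure should be reported as (S)AEs if they meet the protocol specified definitions", and Note 3 does the same for elective stays. Notes 8 and 9 exempt lead migration and device failure, but bring back any AE that results. Note 5 alone limits what it brings back to one cause and one time window.

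**Does the all-SAE rule settle type 2?** Not on the text. Tables 20.2-1 and 17.2-1 define an SAE as an adverse event with certain consequences, and the tables in 20.4 and 17.4 route SAEs through the AE eCRF page. An instruction not to report something as an AE can be read as closing that route. No order of precedence appears in the text available.

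**Size.** Let *s* be the share of device- and procedure-related AEs that are stimulation-related, and *f* the share of those that fall in type 2 or 3 and go unreported. The recorded count is then (1 − *s* × *f*) times the full count, a shortfall of *s* × *f*. The documents give neither *s* nor *f*, nor anything from which to bound them.

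**The case against.** The strongest reply is that the other rules already capture what matters. The all-SAE duty is stated twice in each protocol. Note 5 speaks of sensations or side effects, and a death, a life-threatening injury or an admission is not naturally described that way. For lasting harm from a dropped setting, NAVITAS 20.1 and ENVISION 17.1 tell sites to submit an event when its category is unclear or it cannot be separated from the device or procedure. Note 7 makes clinically significant worsening beyond the pre-SCS state an AE, whatever setting caused it. Source-document review by monitors and classification by the medical safety group (NAVITAS 22.1, ENVISION 19.1) may correct some differences between sites. Leaving out brief sensations during programming is also a reasonable choice, made in advance.

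Much of this stands. A reader might infer that Note 5 removes serious in-session events from the SAE rate. The documents do not support that: they contain an instruction each way, so omission is possible but not prescribed. Likewise, persisting harm from a dropped setting is ambiguous rather than clearly barred.

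The reply does not remove the conflict. The submit-if-unclear rule helps only a site that sees something unclear, and Note 5 is worded as a plain instruction. Note 7 covers worsening of symptoms, and a new injury, such as a fall after a jolt, is not obviously that. Central classification works mainly on events that sites have submitted.

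**Conclusion.** The point holds as an internal contradiction in both protocols. Note 5, read literally, excludes serious in-session events and lasting effects of tested-and-dropped settings, while the reporting sections require them, with no stated precedence. The device-related AE rate and the SAE rate may therefore be under-counted, and by different amounts at different sites. This assumes only that some sites follow the literal wording of Note 5. Omission is explicit only for non-serious effects confined to the session.

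Two further inferences should be resisted. Neither plan states a separate stimulation-related AE rate; these events sit inside the device-related rate, so an under-count among them is diluted there. And no percentage can be attached: any figure for the share of events affected would be an assumption with no anchor in the documents. It is worth correcting because it touches the only result each plan commits to report and the correction is cheap.

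**What to change.** Reconcile Note 5 with 20.1 and 20.4 in NAVITAS and with 17.1 and 17.4 in ENVISION, and carry the same wording into the AE eCRF instructions:

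- Limit the exemption to non-serious effects that resolve within the programming session.
- State that any event that meets an SAE criterion, or that persists after the session, is reported whether the setting responsible was tested or final. The present restriction to final parameters then falls away.
- State in the safety report that transient in-session effects are not counted, so that readers know what the device-related AE rate covers.

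This changes reporting only, not programming or treatment. It costs about one sentence in each protocol and the matching eCRF text. The downside is a few more AE entries and possibly a slightly less favourable device-related AE rate.

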20.3. Relationship to Device(s)

The Investigator must assess the relationship of the reportable AE to the device, or procedure. See criteria in Table 20.3-1.

Table 20.3-1: Criteria for Assessing Relationship of Study Device or Procedure to Adverse Event

Classification	Description
Unrelated	The adverse event is determined to be due to a concurrent illness or effect of another device/drug and is not related to the investigational product.
Related	d) The adverse event is determined to be potentially related to the investigational product, and an alternative etiology is equally or less likely compared to the potential relationship to investigational product, or

Table 20.3-1: Criteria for Assessing Relationship of Study Device or Procedure to Adverse Event

Classification	Description
	e) There is a strong relationship to investigational product, or recurs on re-challenge, and another etiology is unlikely, or There is no other reasonable medical explanation for the event.

The Investigator should assess the potential relationship of the adverse event to the **study device**. All **study device** related adverse events will be assessed according to their relationship to one of the following sub-categories:

- a) **Device hardware-related** AEs will be those that reasonably can be attributed to mere presence of the device or to a malfunction of the device or a deficiency of the device (such as, allergy to device materials). The following criteria are used to determine device hardware-relatedness:
- b) The adverse event is determined to be potentially related to the investigational product, and an alternative etiology is equally or less likely compared to the potential relationship to investigational product, or
- c) There is a strong relationship to investigational product, or recurs on re-challenge, and another etiology is unlikely, or
- d) There is no other reasonable medical explanation for the event.
- e) **Stimulation-related** AEs, will be those that show a relationship to stimulation on and off (such as, undesired sensations). It will also include those that are thought to be stimulation-related, but that relationship cannot be demonstrated with stimulation on/off.

The Investigator should also assess the potential relationship of the adverse event to the **study procedure**.

20.4. Investigator Reporting Requirements

The communication requirements for reporting to BSC are as shown below.

Event Classification	Communication Method	Communication Timeline
Serious Adverse Event including Serious Adverse Device Effects	Complete AE eCRF page with all available new and updated information	
 • Within 2 business days of first becoming aware of the event or as per local/regional regulations. • Reporting required through the end of the study

Event Classification	Communication Method	Communication Timeline
	Provide all relevant source documentation (unidentified) for reported event	
 When documentation is available
Adverse Event	Complete AE eCRF page, which contains such information as date of AE, treatment of AE resolution, assessment of seriousness and relationship to the device	
 In a timely manner after becoming aware of the information Reporting required through end of study participation Only device-related and procedure-related adverse events
Device Deficiencies (including but not limited to failures, malfunctions, and product nonconformities) Note: Any Device Deficiency that might have led to a serious adverse event if a) suitable action had not been taken or b) intervention had not been made or c) if circumstances had been less fortunate is considered a reportable event.	
Complete Device Deficiency CRF with all available new and updated information.
 
Complete Device Deficiency eCRF with all available new and updated information
	
 Within 2 business days of first becoming aware of the event. Reporting required through the end of the study For Device Deficiency that might have led to a serious adverse event if a) suitable action had not been taken or b) intervention had not been made or c) if circumstances had been less fortunate is considered a reportable event reporting required within 2 business days of first becoming aware of the event and as per local/regional regulations Reporting required through the end of the study

The investigator must report Device and Procedure Related Adverse Events, Adverse Device Effects, Serious Adverse Events (regardless of relationship to device hardware, stimulation and/or procedure), Unanticipated Adverse Device Effects, and Device Deficiencies for each subject from the time of Information Consent through the end of study participation. AEs and Device Deficiencies may be reported via phone, fax or email if the electronic data capture (EDC) system is unavailable. The paper AE Notification Form or Device Deficiency Notification Form should be used to report AEs and/or device deficiencies during this time.

The Investigator must assess the potential relationship of all adverse events to the study device and/or to study procedures.

- Adverse events must be assessed according to their relationship to one of the following categories:
 - Device Hardware-Related AEs:** AEs that can reasonably (i.e. Unlikely, Possibly, Probably and Causally Related) be attributed to the mere physical presence of the device or to deficiency of the device (i.e., an allergic response to device materials).

- **Stimulation-Related AEs:** AEs that can reasonably (i.e. Unlikely, Possibly, Probably and Causally Related) be attributed to the effects of stimulation. A relationship to stimulation may be determined by demonstrating a predictable response to the alternating between stimulation-on and stimulation-off settings. However, a relationship to stimulation may also be reported without demonstrating a predictable response to the alternating between the stimulation-on and stimulation-off settings if in the opinion of the Investigator the AE is potentially related to stimulation.
- **Procedure Related AEs:** AEs that can reasonably (i.e. Unlikely, Possibly, Probably and Causally Related) be attributed to a study protocol required procedure.

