NAVITAS Study

A Study to Characterize the Relationship between Select Objective Metrics and Clinical Outcomes in Chronic Pain Patients treated with Boston Scientific Neurostimulation Systems

CLINICAL INVESTIGATION PLAN

Sub-Study
TO THE RELIEF STUDY PROTOCOL
A7007

Sponsored By

Boston Scientific Corporation
Neuromodulation
[name]
[name]
United States of America

This protocol contains confidential information for use by the Investigators and their designated representatives participating in this clinical investigation. The protocol should be held confidential and maintained in a secure location.

[figure not shown]
Do not copy or distribute without written permission from Boston Scientific Corporation.

[figure not shown]
Contact Information

[figure not shown]
Role	Contact

Original Release: 28APR2017

Current Version: 24JUL2019

2. Protocol Synopsis

NAVITAS: A Study to Characterize the Relationship between Select Objective Metrics and Clinical Outcomes in Chronic Pain Patients treated with Boston Scientific Neurostimulation Systems

The NAVITAS Sub-study is being conducted under the RELIEF Study however subjects enrolled in NAVITAS will follow protocol requirements within this document only. Subjects enrolled in the NAVITAS protocol will not be enrolled in the RELIEF study and should be withdrawn from RELIEF if they are already enrolled.

Study Objective(s)	The objective of the study is to characterize the relationship between select objective metrics and clinical outcomes in chronic pain patients treated with Boston Scientific commercially approved neurostimulation systems.
Devices	All commercially approved Boston Scientific neurostimulation systems indicated for the treatment of chronic pain, with the exception of Precision™ and Precision™ Plus. All commercially approved VitalConnect™ Sensor indicated for continuous collection of physiological data in home and healthcare settings used as part of the physIQ VitaLink Solution (“Platform”).
Study Design	Prospective, post-market, non-randomized, multi-center study
Planned Number of Investigational Sites / Countries	The study will be conducted at up to 30 sites in the United States

NAVITAS: A Study to Characterize the Relationship between Select Objective Metrics and Clinical Outcomes in Chronic Pain Patients treated with Boston Scientific Neurostimulation Systems

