7.1. Safety Parameters

The rate of neurostimulator device and procedure-related adverse events (AEs), Serious Adverse Events (SAEs), from informed consent through study exit will be reported.

8. Study Design

The NAVITAS Study is a prospective, post-market, non-randomized, multi-center, study.

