22.1. Safety Monitoring Process

The BSC Medical Safety group reviews unmonitored data as soon as the event is reported, on a continuous basis. During scheduled monitoring activities, clinical research monitors will support this continuous review through their review of source document and other data information. The BSC Medical Safety group includes a board-certified physician with expertise in neurology and neuromodulation and with the necessary therapeutic and subject matter expertise to evaluate and classify the events into the categories outlined above.

23. Suspension or Termination

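### NAVITAS sections 20.3 and 20.4 set conflicting tests for a device hardware-related adverse event, so the visible text gives no single counting rule for the related-AE rate promised in 7.1

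*Combined protocol and SAP*

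**What the plan says.** **The commitment.** NAVITAS 7.1: "The rate of neurostimulator device and procedure-related adverse events (AEs), Serious Adverse Events (SAEs), from informed consent through study exit will be reported".

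**First test (20.3).** Table 20.3-1 has two classes, Unrelated and Related. The least demanding route to Related reads "The adverse event is determined to be potentially related to the investigational product, and an alternative etiology is equally or less likely compared" with the link to the product. The other two routes need a strong relationship with another cause unlikely, or the absence of any other reasonable medical explanation. The section then repeats the three routes for hardware events, introduced by "The following criteria are used to determine device hardware-relatedness".

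**Second test (20.4).** Adverse events must be assessed into three categories. Device Hardware-Related AEs are "AEs that can reasonably (i.e. Unlikely, Possibly, Probably and Causally Related) be attributed to the mere physical presence of the device" or to a deficiency of the device. Procedure Related AEs are "AEs that can reasonably (i.e. Unlikely, Possibly, Probably and Causally Related) be attributed to a study protocol required procedure".

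**What must be sent in.** The 20.4 reporting table limits non-serious reporting to device-related and procedure-related events. Serious events are reported whatever their relationship.

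**Which document governs.** The synopsis says that "subjects enrolled in NAVITAS will follow protocol requirements within this document only".

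**The concern.** The two sections name the same category and use mandatory language, but draw the line in different places. This is a contradiction in current, visible text and does not depend on anything blacked out.

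The rate in 7.1 is the only outcome rate that the visible plan promises; there are no pre-defined endpoints. If its counting rule is ambiguous, two careful analysts can report different related-AE rates from the same database. Two sites can also build different databases, because the relatedness judgement decides whether a non-serious event is submitted at all. An event never submitted cannot be recovered by recoding.

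**Working it through.** The plan states no adverse event rate, so there is no figure to reproduce. The check is a comparison of the texts.

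1. *Same category?* Yes. Both sections define device hardware-related events by name.
2. *Same scale?* No. 20.3 has two classes; 20.4 lists four grades: Unlikely, Possibly, Probably and Causally Related.
3. *Test case.* Take an event for which another cause is judged more likely than the device.
   - Under 20.3 it fails the first criterion, because the alternative is neither equally nor less likely. It fails the second, because another cause is not unlikely, and the third, because another reasonable explanation exists. With only two classes, it is not Related.
   - Under 20.4, on the ordinary meaning of the word, it is graded Unlikely. That grade is on the list, so it counts as hardware-related.
4. *Can the grades be read from elsewhere?* Not in the visible NAVITAS text. ENVISION Table 17.3-1 defines them, but NAVITAS subjects follow the NAVITAS document alone. Without definitions it is not even certain that the 20.3 line falls exactly between Unlikely and Possibly.
5. *Effect on collection.* A site using 20.3 could leave the non-serious test event unreported; a site using 20.4 would submit it.
6. *Effect on the rate.* For a fixed set of submitted events, the rate under 20.4 minus the rate under 20.3 equals A/N. Here A is the number of subjects (or events) that qualify under 20.4 but not under 20.3, and N is the denominator. A cannot be negative, since anything meeting a 20.3 criterion would ordinarily be graded Possibly or higher. The visible text gives neither A nor N, and does not say whether the rate is per subject or per event. The direction is known; the size is not.
7. *Where the conflict is weaker.* For stimulation, 20.3 already accepts events merely thought to be stimulation-related. For procedures, it asks for an assessment, but the table's criteria name only the investigational product.

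Two related wording points:

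- *Procedure.* 13.2.11 and 20.3 speak of the study procedure; 20.4 speaks of one that the protocol requires. Implantation is optional and follows routine care (8.2.1; 20.2, Note 2), so the 20.4 phrase does not expressly cover it.
- *Safety set.* 12.3 says that all consented subjects enter the analyses, then that wearers of a chest or wrist sensor enter the safety analyses. Neither sentence is tied to neurostimulator exposure, although 12.2.2 foresees consented patients who never reach a trial.

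**The case against.** The best defence is that 20.4 is headed as reporting requirements and can be read as a deliberately wide collection net, with 20.3 supplying the causality judgement. Two other provisions help. Section 20.1 covers doubtful cases ("If it is unclear whether an event fits one of the above categories") by asking for submission, and under 22.1 the sponsor's Medical Safety group is equipped to "evaluate and classify the events into the categories outlined above". These do reduce the risk of under-reporting and of uneven classification. But 20.4 says that events must be assessed into its categories, not merely sent in, and neither provision says which grades enter the 7.1 rate.

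Some stronger readings are tempting but not supported:

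- *That adverse events of the implant procedure drop out.* Note 2 in 20.2 goes on to say that complications of a planned routine-care procedure are to be reported if they meet the definitions. Section 13.2.28 collects all trial and implantation procedures, both are scheduled visits (11.6, 11.9), and 20.1 covers events during or after the procedure. The intent to capture them is fairly clear; only the 20.4 wording is loose.
- *That 12.3 restricts safety analyses to sensor wearers.* The sentence contains no limiting word and can be read as additive. Sensors are provided to all enrolled patients (12.2.2), and De Novo wear starts in the baseline period, before the trial procedure.
- *That the plan lacks a denominator.* NAVITAS 12.2 is blacked out. Sections 10.3 and 12.3.1 to 12.3.5, and the subject classification section cited in 20.1, are not visible. A denominator may be set there.
- *That ENVISION has the same fault.* Its Table 17.3-1 defines the grades and keeps Unlikely Related on purpose, so its scales do not conflict.
- *That the 1,400 and 960 limits in 10.4 bound the effect.* They are alternative stopping limits for enrollment and implants, not a planned implant share.

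**Conclusion.** The conflict between 20.3 and 20.4 is real and clearest for hardware-related events. As written, the same event can be related or unrelated depending on which section is applied, and this can alter both what sites submit and the rate promised in 7.1.

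Its size cannot be derived and no figure should be attached to it. It depends on how many subjects or events qualify only through the Unlikely grade. The conclusion assumes that Unlikely has its ordinary meaning of a more probable alternative cause.

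Severity is minor. NAVITAS has no formal hypotheses, no powered endpoints and no decision threshold on this rate, and an all-SAE count does not depend on relatedness. What suffers is the clarity and comparability of one reported safety figure. The procedure and sensor-wear points are secondary and subject to the sections that cannot be seen.

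**What to change.** **Main change.** Reconcile NAVITAS 20.3 and 20.4 to a single causality scale and define each grade in the NAVITAS document. Keep events graded Unlikely reportable, but tabulate them separately and exclude them from the headline related-AE rate in 7.1.

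**Secondary wording.**
- In 20.4, replace the reference to a procedure required by the protocol with wording that expressly includes neurostimulation trial, implant and revision procedures, in line with 13.2.28 and Note 2 of 20.2.
- In 12.3, do not make inclusion in the neurostimulator safety analyses depend on sensor wear. Show the device-related rate also among subjects exposed to neurostimulation, unless sections that are not visible already do this.

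No change to ENVISION is needed on this point.

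**Cost.** Wording changes in 12.3, 20.3 and 20.4, and one recoded adverse event table, with an exposed-subject rate added if it is not already planned. The headline related-AE percentage may fall slightly. Events already collected can be split only if the grade was captured at the time; those recorded on the two-class scale cannot be regraded from the database alone.
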